CS1170 Rev D Clinical Study Synopsis

FARA-FREEDOM: A Prospective Open-Label Single Arm Post Market Clinical Follow-Up Trial of the FARAPULSE Pulsed Field Ablation System in Patients with Paroxysmal Atrial Fibrillation

SPONSOR: FARAPULSE, INC. [name]

ISSUE DATE: 18MAY 2022

This study is to be performed in accordance with Good Clinical Practice (GCP), the ethical principles that have their origin in the Declaration of Helsinki, International Conference on Harmonisation E6 and ANSI / AAMI / ISO Standards 14155:2020.

This document contains confidential and proprietary information and may not be copied or reproduced in whole or in part without the express written permission of FARAPULSE, INC., MENLO PARK, CA.

CONFIDENTIAL

© 2022, Farapulse, Inc.

MAY 18, 2022 PAGE 2

Revision History

Rev	DCO	Description of Changes	Effective Date	Prepared By		
В	21-289	To match the updated protocol	18Aug2021	[name]		
В	21-302	Administrative changes: Deleted "in either the Pulsed Field or Thermal Groups" In section 5.2 Index Procedure, Pg #4 which was inadvertently missed during the review of the document. Formatted document throughout to have same font and size for consistency.	27 Aug 2021	[name]		
C	21-323	Aligning with the protocol change	19Sep2021	[name]		
D	22-126	Aligning with the protocol change Page #3: Update to reflect the increase in total sites from 15 to 25 Page #11: CT was added as approved procedure to exclude presence of LAA thrombus	18 May 2022	[name]		

Executive Summary

SPONSOR NAME:	FARAPULSE, Inc.					
TITLE OF STUDY:	A Prospective Open-Label Single Arm Post Market Clinical Follow-Up Trial of the FARAPULSE Pulsed Field Ablation System in Patients with Paroxysmal Atrial Fibrillation					
REFERENCE CIP NUMBER / REVISION:	CS1169 Rev D					
Objective:	The purpose of the study is to provide ongoing post-market demonstration of the safety and performance of the FARAPULSE Pulsed Field Ablation System in the treatment of patients with paroxysmal atrial fibrillation (PAF).					
NAME OF	FARAPULSE Pulsed Field Ablation System					
INVESTIGATIONAL DEVICE:	 FARAWAVE[™] Pulsed Field Ablation Catheter FARASTAR[™] Pulsed Field Ablation Generator FARADRIVE[™] Steerable Sheath 					
DESIGN:	Subjects will undergo percutaneous endocardial ablation for pulmonary vein isolation using the FARAPULSE Pulsed Field Ablation System. Subjects with typical right-sided (isthmus- dependent) atrial flutter (AFL) may undergo ablative interruption of the cavo-tricuspid isthmus (CTI). Class I / III antiarrhythmic drugs (AADs) will be discontinued at Day 60 ± 10 , subject to Investigator discretion Subjects will then be followed at 7 days, 30 days, 90 days, 6 months, and 12 months for adverse events (AEs), : Subjects will be monitored with weekly scheduled plus symptom-driven event monitoring, as well as 6 and 12-month Holter monitoring, for freedom from recurrent arrhythmia (atrial fibrillation [AF], AFL or atrial tachycardia [AT]) after the Blanking Period (Days 0 - 90).					
STUDY POPULATION:	Subjects with documented PAF who have had ≥ 2 episodes within 6 months of enrollment.					
Planned Enrollment:	180 subjects					
CLINICAL SITES:	Up to 25 enrolling centers.					

DURATION OF SUBJECT PARTICIPATION:	The enrollment period is estimated to take 12 months and subjects will be followed for up to 13 months. There will be a 3-month period of site close-out visits, for a planned study duration of approximately 34 months Coronavirus Disease 2019 (COVID 19)-related disruptions may alter this timeframe . Subject participation is anticipated to be 13 ± 1 months to allow for screening, pre-procedural diagnostic procedures, treatment and 12 ± 1 months of study follow-up.					
PLANNED PROCEDURES:	 Index Procedure / Rescheduled Index Procedure: All subjects will be screened for atrial thrombus just prior to or at the time of the Index Procedure and will be rescheduled if positive. PVI: Subjects will undergo an attempt to isolate all pulmonary veins or their anatomic equivalent with the FARAPULSE Pulsed Field Ablation System. CTI: Subjects with a past history of CTI-mediated (typical) AFL, who manifest typical AFL during a procedure or within the Blanking Period, or who have inducible typical flutter, may undergo ablation of the CTI at the discretion of the Investigator using any approved RF catheter during the Index / Rescheduled Index Procedure or any reablation procedure. Other Ablation: Other ablation is not permitted under this protocol except when the Investigator determines that subject welfare requires ablation for an accessory pathway, atrioventricular nodal reentrant tachycardia (AVNRT), treatment-emergent left-sided AFL or incessant AT. 					
RE-ABLATION PROCEDURE	Re-ablation under this protocol requires documentation of Detectable AF, AFL or AT.Any re-ablation procedure for AF, AFL or AT during study follow-up constitutes a Treatment Failure.However, CTI ablation or re-ablation for right-sided typical AFL may be performed at any time during study follow-up and does not constitute a Treatment Failure.					

ANTIARRHYTHMIC DRUGS	 Antiarrhythmic drugs (AADs), except for amiodarone, may be utilized during the Blanking Period at the Investigator's discretion. On Day 60 ± 10 each subject will be contacted by telephone to stop all AADs. Class I / III AADs should be stopped at the Day 60 Assessment. However, at the Investigator's discretion, Class I / III AADs may be continued up to Day 90 without creating a primary performance endpoint failure. The use of amiodarone at any time during the study, except intraprocedurally to control an arrhythmia, or the use of Class I / III AADs after Day 90, constitute a Treatment Failure. 					
PRIMARY SAFETY ENDPOINT:	The primary safety endpoint is the Composite Safety Endpoint (CSE) defined as the proportion of Safety Subjects with one or more of the following device- or procedure-related SAEs as adjudicated by the CEC based on protocol definitions. Early onset (within 7 days of an index or Rescheduled Index procedure: • Death • Myocardial infarction • Persistent phrenic nerve palsy • Stroke • Transient ischemic attack (TIA) • Peripheral or organ thromboembolism • Cardiac tamponade / perforation • Pericarditis • Pulmonary edema • Vascular access complications • Heart block • Gastric motility/pyloric spasm disorders Late onset (any time through the completion of 12 month follow-up visit) • Pulmonary vein stenosis • Atrio-esophageal fistula					
Additional Safety Analyses:	 Severe Ablation Complications Nonserious / Serious CSEs Post-Blanking Direct Current Cardioversions Post-Blanking Arrhythmia Hospitalizations Any Related SAE Any Related Stroke or TIA 					

PRIMARY EFFECTIVENESS ENDPOINT:	 The primary performance endpoint is Treatment Success in Modified Intent-to-Treat (mITT) subjects, defined as: Acute Procedural Success, AND 1. Chronic Success, defined as freedom from: a. At the Index / Rescheduled Index Procedure: Use of a non-PFA treatment modality for PVI b. After the Blanking Period: i. Occurrence of any Detectable AF, AFL or AT (excluding CTI-dependent AFL confirmed by EP study) ii. Cardioversion for AF, AFL or AT (excluding for CTI-dependent AFL) iii. Use of any Type I or Type III antiarrhythmic medication for the treatment of AF, AFL or AT c. At any time: i. Re-ablation for AF, AFL or AT (other than for CTI-dependent AFL)
Additional Effectiveness Analyses:	 Acute Procedural Success Acute Vein Success Chronic Success Chronic Success Allowing Re-ablation Chronic Success Allowing AADs Treatment Success Allowing Re-ablation Treatment Success Allowing AADs Treatment Success with PVI/CTI Only Early Recurrence of AF Rate of Re-ablation AF Symptom Assessment
PROCEDURAL Assessments:	 Assessments of duration for procedure components a. Procedure time (initiation of venous access to venous access closure). b. Left atrial dwell time (total time an ablation catheter is in the left atrium [LA]) c. Total ablation time (first ablation to last ablation) d. Fluoroscopy time (total duration of exposure). Characterization of lesion sets: a. PVI ablations b. CTI ablations c. For subjects undergoing required LA ablations for an accessory pathway, AVNRT, left-sided AFL or incessant AT, a description of lesion sets utilized
QUALITY OF LIFE MEASURES	Subjects will undergo assessment with the EQ-5D-3 L instrument and Atrial Fibrillation Effect on Quality of Life (AFEQT) questionnaire at baseline and 12 months.

	1				
SAMPLE SIZE Considerations	Sample size requirements for safety: Sample size is estimated assuming an underlying CSE rate of 9% compared to a performance goal (PG) of 17% using a binomial exact test. Assuming 80% power and one-sided Type I error of 2.5%, a minimum sample size of 150 is required.				
	Sample size requirements for performance: Sample size is estimated assuming an expected percent success of 65% compared to a PG of 50% using a binomial exact test. Assuming 80% power and one-sided Type I error of 2.5%, a minimum sample size of 85 is required.				
	Number of subjects: The sample requires 150 analyzable subjects to meet both safety and performance calculations. To allow for up to 15% subject losses, the study size has been set at approximately 180 subjects.				
Clinical Events Committee	An independent panel of 3 electrophysiologists will review AEs, adjudicate seriousness and relatedness of potential SAEs and adjudicate primary safety and performance outcomes.				
ARRHYTHMIA CORE Laboratory	A qualified Arrhythmia Core Lab (ACL) will be established to receive, review and assess all protocol-stipulated ECGs, EMs and Holter monitors.				
INCLUSION CRITERIA:	 Study subjects are required to meet all the following inclusion criteria to participate in this study: 1. Patients with PAF that meets all the following criteria: a. Paroxysmal: AF that terminates spontaneously or with intervention within 7 days of onset. b. Frequency: i. Physician documentation of recurrent PAF (two or more episodes) within 6 months, AND ii. At least one (1) documented episode by an approved recording device within 12 months of enrollment c. Drug Failed atrial fibrillation drug (AAD) treatment, meaning therapeutic failure of at least one AAD (class I – IV) for efficacy and / or intolerance. 				
	 2.Patients who are ≥ 18 and ≤ 80 years of age on the day of enrollment. 3. Patient participation requirements: a. Is willing and capable of providing Informed Consent to undergo study procedures. b. Is willing to participate in all examinations and follow-up visits and tests associated with this clinical study. 				

EXCLUSION CRITERIA:	Subjects will be excluded from participating in this study if they meet any one of the following exclusion criteria:
	 Atrial fibrillation that is any of the following: Persistent (both early and longstanding) by diagnosis or continuous duration > 7 days Secondary to electrolyte imbalance, thyroid disease, alcohol or other reversible / non-cardiac causes Requires four (4) or more direct-current cardioversions in the preceding 12 months Any of the following atrial conditions: Left atrial anteroposterior diameter ≥ 5.5 cm Any prior atrial endocardial or epicardial ablation procedure, other than right sided cavotricuspid isthmus ablation or for right sided SVT Any prior atrial surgery Interatrial septal patch or interatrial shunt Atrial myxoma Current LA thrombus LA appendage closure, device or occlusion Any PV abnormality, stenosis or stenting (common and middle PVs are admissible)
	 3. At any time, one or more of the following cardiovascular procedures, implants or conditions: a. Sustained ventricular tachycardia or any ventricular fibrillation b. Hemodynamically significant valvular disease c. Clinically significant hypertrophic cardiomyopathy d. Any prosthetic heart valve, ring or repair including balloon aortic valvuloplasty e. Contraindication to femoral venous access
	 4. Any of the following procedures, implants or conditions: a. At baseline: i. Congestive heart failure with New York Heart Association (NYHA) Class III or IV ii. Left ventricular ejection fraction (LVEF) < 35% iii. Uncontrolled hypertension (SBP > 160 mmHg or DBP > 95 mmHg on two BP measurements at baseline assessment) iv. Implantable loop recorder or insertable cardiac monitor b. Within the 3 months preceding the Consent Date: i. Myocardial infarction ii. Unstable angina
	 iii. Percutaneous coronary intervention iv. Implantation of a pacemaker, cardioverter defibrillator or cardiac resynchronization therapy device v. Heart failure hospitalization vi. Treatment with amiodarone vii. Pericarditis or symptomatic pericardial effusion

MAY 18, 2022 PAGE 9

Γ	
	viii. Gastrointestinal bleeding
	c. Within the 6 months preceding the Consent Date:
	i. Heart surgery
	ii. Stroke, TIA or intracranial bleedingiii. Any thromboembolic event
	iv. Carotid stenting or endarterectomy
	IV. Carotid schung of characterionity
	5. Diagnosed disorder of blood clotting or bleeding diathesis
	6. Contraindication to, or unwillingness to use, systemic anticoagulation
	7. Patient who is not on anticoagulation therapy for at least 3 weeks prior to the ablation procedure
	8. Women of childbearing potential who are pregnant, lactating, not
	using birth control or planning to become pregnant during the
	anticipated study period
	9. Medical conditions that would prevent participation in the study,
	interfere with assessment or therapy, significantly raise the risk of
	study participation, or confound data or its interpretation, including but not limited to:
	a. Body mass index $(BMI) > 45.0$
	b. Solid organ or hematologic transplant, or currently being
	evaluated for an organ transplant
	c. Severe lung disease, pulmonary hypertension, or any lung
	disease associated with chronic abnormal blood gases or requiring supplemental oxygen
	d. Renal insufficiency with an estimated glomerular filtration rate
	$(eGFR) < 30 \text{ mL/min/1.73 m}^2$, or any history of renal dialysis
	or renal transplant
	e. Active malignancy or history of treated malignancy within 24
	months of enrollment (other than cutaneous basal cell or
	squamous cell carcinoma)
	f. Active systemic infection
	g. COVID-19 disease
	I. Current confirmed, active COVID-19 disease
	II. Current positive test for SARS-CoV-2
	III. Confirmed COVID-19 disease not clinically resolved at least 3 months prior to the Consent Date
	h. Other uncontrolled medical conditions that may modify
	device effect or increase risk, including uncontrolled diabetes
	mellitus, untreated sleep apnea or active alcohol abuse
	i. Predicted life expectancy less than one (1) year
	1 2 (7)

FARAPULSE FARA-FREEDOM CLINICAL STUDY SYNOPSIS CS1170, REVISION D

MAY 18, 2022 PAGE 10

Exclusion Criteria (continued):	 10. Clinically significant psychological condition that in the investigator's opinion would prohibit the subject's ability to meet the protocol requirements. 11. Current or anticipated enrollment in any other clinical study. (data collection for registries or retrospective studies is permitted)
------------------------------------	--------------------------------------------------------------------------------------------------------------------------------------------------------------------------------------------------------------------------------------------------------------------------------------------------------------------------------------

MAY 18, 2022 PAGE 11

Schedule of Event

Assessment	Baseline ¹	Index Procedure	Pre- Discharge	Day 7 (7-11 days)	Day 30 (± 7 days)	Day 60 (± 10 days)	Re- Ablation Procedures	Day 90 (90 ± 14 days)	Month 6 (180 ± 30 days)	Month 12 (360 ± 30 days)	Unscheduled
Informed consent, baseline assessments	X^2										
Anti-arrhythmic drugs (AADs)	Х		Х	Х	Х	D/C AADs	Х	Х	X	Х	Х
Recurrent arrhythmia, cardioversions, ablations, hospital admissions			Х	Х	Х		Х	Х	X	Х	Х
Pregnancy test	X ³	X ³					X ³				
12-lead ECG	Х		Х					Х	Х	Х	Х
Event monitors	Training		Training					Weekly + symptomatic transmissions		Х	
72-Hour continuous ECG (Holter)	Training		Training						X	Х	
TEE/CT/ICE to exclude LA thrombus		X ⁴					X ⁴				
NIHSS	Х		Х								
Radiologic examination of diaphragm		Х					X	X ⁵	X ⁵	X^5	
Post-procedure assessments of PVI and CTI ablation		Х					Х				
AF Symptom, EQ-5D-3 L and AFEQT assessments	Х									Х	
Neuro assessment			X ⁶								
Adverse events		Х	Х	Х	Х		Х	Х	Х	Х	Х

 All Baseline Assessments must be generated in the window beginning 30 days prior to the Consent Date and ending on the date of the Index Procedure.
 Baseline assessments include the inclusion/exclusion criteria and the data stipulated in Section 4.6.1
 Females of childbearing potential only. The pre-procedural pregnancy test is not required if the Index Procedure / Rescheduled Index Procedure is within 30 days of the baseline pregnancy test.

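### The drug-failure component of the primary performance endpoint is defined inconsistently: two sections of the protocol synopsis disagree, and the SAP endpoint has no drug item

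*Protocol*

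**What the plan says.** **Protocol synopsis, Antiarrhythmic Drugs.** Drug use up to Day 90 is tolerated: "Class I / III AADs may be continued up to Day 90 without creating a primary performance endpoint failure". After that, "the use of Class I / III AADs after Day 90, constitute a Treatment Failure", with no mention of why the drug was given. The same sentence puts amiodarone on a different clock: "The use of amiodarone at any time during the study, except intraprocedurally to control an arrhythmia" is also a Treatment Failure.

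**Protocol synopsis, Primary Effectiveness Endpoint.** Treatment Success needs Acute Procedural Success and Chronic Success, and Chronic Success means that none of the listed events occurs. The post-blanking events are:
- b.i: "Occurrence of any Detectable AF, AFL or AT (excluding CTI-dependent AFL confirmed by EP study")
- b.ii: "Cardioversion for AF, AFL or AT (excluding for CTI-dependent AFL")
- b.iii: "Use of any Type I or Type III antiarrhythmic medication for the treatment of AF, AFL or AT"

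Item c, which applies at all times, contains only re-ablation and again leaves out CTI-dependent flutter.

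**Protocol synopsis, Design.** Freedom from recurrence is assessed "after the Blanking Period (Days 0 - 90"), so post-blanking and after Day 90 are the same period.

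**SAP section 2.1.3.** The primary effectiveness endpoint fails on post-blanking arrhythmia or on ablation. It lists no drug event. Section 2.1.4, item 2, gives the endpoint for subjects off AFDs, an abbreviation that the SAP does not define, as an additional outcome counted from Day 105.

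**The concern.** The Clinical Events Committee adjudicates the primary performance outcome. For some drug exposures the synopsis gives it two answers, and nothing in the supplied documents says which section prevails. The SAP cannot settle the matter, because its endpoint ignores drugs.

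The trial has one arm and tests against a fixed 50% goal, so no control group absorbs a change of definition: a stricter or looser drug rule goes straight into the success proportion. If the rule is still open when the data are in, the choice can be made, or can appear to have been made, with the result in view. The documents also do not say which drug rule the assumed 65% success and the 50% goal presuppose.

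**Working it through.** **Step 1. Align the periods.** Blanking is Days 0 to 90, so item b.iii and the Class I/III clause of the Antiarrhythmic Drugs section both start on Day 91. For that clause the two sections differ in indication, not in timing.

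**Step 2. Classify each exposure under each text.** Each entry asks whether the drug use alone makes the subject a failure.

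| Exposure | Antiarrhythmic Drugs section | Endpoint items b and c | SAP 2.1.3 |
|---|---|---|---|
| Class I/III after Day 90 for AF, AT or flutter that is not CTI-dependent | Failure | Failure (b.iii) | Not a failure |
| Class I/III after Day 90 for CTI-dependent flutter | Failure | Failure (b.iii) | Not a failure |
| Class I/III after Day 90 for another indication | Failure | Not a failure | Not a failure |
| Amiodarone in Days 0 to 90, not intraprocedural | Failure | Not a failure | Not a failure |
| Other Class I/III up to Day 90 | Not a failure | Not a failure | Not a failure |

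Rows 3 and 4 are contradictions within the synopsis. Rows 1 to 4 all differ between at least one protocol section and the SAP. In row 4, b.iii does not reach the exposure because it starts only after blanking, and item c does not reach it because it lists only re-ablation. The table leaves aside intraprocedural amiodarone, which only the Antiarrhythmic Drugs section mentions.

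**Step 3. The SAP's additional outcome does not fill the gap.** It starts at Day 105. The Day 90 visit window closes at 90 + 14 = 104, which may explain the choice, but drug use on Days 91 to 104 is then outside that outcome while the protocol counts it.

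**Step 4. Size. First, the plan's own figure.** Inputs from Sample Size Considerations: success 65%, goal 50%, power 80%, one-sided 2.5%. The normal approximation gives

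n = ((1.9600 × √(0.5 × 0.5) + 0.8416 × √(0.65 × 0.35)) / 0.15)² = 84.8, rounded up to 85.

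This matches the stated 85. The exact binomial test that the plan names gives 73.6% power at 85 (at least 53 successes needed) and first reaches 80% at n = 90 (at least 55; 81.2%). This is background only: safety sets the requirement at 150 analyzable subjects.

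**Step 5. Decision threshold at 150.** The smallest count r with P(X ≥ r | n = 150, p = 0.5) ≤ 0.025 is 88 (tail probability 0.0204), and 88/150 = 58.7%. Expected successes at 65% are 0.65 × 150 = 97.5, which is 9.5 above the threshold. One reclassified subject is 1/150 = 0.67 points (1/180 = 0.56 points if all 180 are analyzed).

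**Step 6. Sensitivity of power.** The documents give no share of subjects affected. Assume that the stricter reading lowers true success from 65% by the amount shown:

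| Drop in true success | Subjects at n = 150 | Power, n = 150 (≥ 88) | Power, n = 180 (≥ 104) |
|---|---|---|---|
| 0 points | 0 | 95.5% | 98.2% |
| 1 point | 1.5 | 92.5% | 96.4% |
| 2 points | 3.0 | 88.1% | 93.6% |
| 3 points | 4.5 | 82.3% | 89.3% |
| 5 points | 7.5 | 66.3% | 75.4% |

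Only subjects who would otherwise be successes contribute to the drop.

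**The case against.** **The affected group is small.** This largely stands for the conflict inside the synopsis. The planned procedures foresee AVNRT and accessory pathways as reasons for ablation, not for later drug treatment, and the exclusion criteria remove sustained ventricular tachycardia and any ventricular fibrillation. Few subjects may receive a Class I/III drug after Day 90 for a reason other than AF, AFL or AT. The argument does not cover the difference from the SAP, which affects every subject kept on such a drug without a recorded recurrence or ablation.

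**The synopsis already plans Chronic Success and Treatment Success allowing AADs.** Judging by their titles, these relax the drug component and would help to bracket the result. They do not say which rule defines the primary result.

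**The full plan may settle it.** The synopsis refers to a CIP that was not supplied, and the supplied SAP (version 1.1, December 2020) carries the FARA-FREE II study name and predates the May 2022 synopsis. A fuller rule may exist. The synopsis still contradicts itself, and the only SAP supplied omits the component.

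**A stronger reading that the documents do not support.** Because b.iii lacks the CTI exclusion, a reader might infer that one Class I/III dose for CTI-dependent flutter can be a success or a failure: exempt as a cardioversion under b.ii, a failure under b.iii. That does not follow. Chronic Success requires freedom from every item, so the b.ii exclusion only stops b.ii from triggering and gives no protection from b.iii. Such use is a failure under both protocol sections. Nor do the documents show that an intent has been broken. A Class I/III drug may also suppress AF, so counting it whatever the flutter type could be deliberate, and it works against the device. What remains is an asymmetry without a stated reason, and some doubt whether b.ii, which does not specify direct current as the synopsis does elsewhere, is meant to include drug conversion.

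**Conclusion.** The point holds as an inconsistency in the definition of a primary endpoint component. Two exposures get opposite classifications within the synopsis: Class I/III use after Day 90 for an indication other than AF, AFL or AT, and non-intraprocedural amiodarone during blanking. Under the SAP, drug use alone is never a primary failure. The missing CTI exclusion in b.iii is a separate matter for clarification and not a contradiction.

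The size cannot be estimated from the documents. A reader might be tempted to count everyone treated with a Class I/III drug for CTI-dependent flutter among those who change class, but between the two protocol sections they do not. At the assumed 65%, the trial has room for a few reclassifications at n = 150: power stays above 80% for a loss of up to 3 points and falls to 66.3% for a loss of 5. The figures assume the protocol's exact binomial test on a proportion; the SAP instead plans a Kaplan-Meier estimate at Day 365, for which 88 successes is only a guide. The inconsistency should be removed before analysis, but it does not by itself threaten the trial.

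**What to change.** 1. Reconcile the Antiarrhythmic Drugs section, item b.iii and SAP sections 2.1.3 and 2.1.4 into one classification rule, worded identically in protocol and SAP. It should fix the indications covered, the first day that counts and how amiodarone during blanking is classified.
2. State whether Class I/III use for CTI-dependent flutter counts as a failure, either way, and whether drug conversion falls under b.ii or b.iii.
3. Make sure that the indication for each Class I/III use after Day 90 is recorded. The Schedule of Events already collects AADs at most visits; whether the case report form captures the reason cannot be seen from the documents.
4. Report the primary endpoint under the alternative reading as a sensitivity analysis.

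The cost is wording in the synopsis, CIP, SAP and committee charter, possibly one data field, and one table. The downside is that the success rate may shift slightly in either direction. The change concerns endpoint classification only; it neither alters nor judges which drugs subjects may receive.
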